2. OBJECTIVES

2.1. General:

Compare intraoperative hemodynamic changes (cardiac output, blood pressure, heart rate, oxygen saturation) and cerebral oxygenation using peripheral cerebral saturation monitoring and continuous hemodynamic measurement of cardiac output or standard hemodynamics monitoring between two anesthetic techniques for shoulder surgery: interscalene block with sedation versus interscalene block with general anesthesia.

2.2. Specifics:

- Compare changes in cerebral tissue saturation between groups;
- Assess delirium and behavioral changes;
- Verify the superiority of continuous hemodynamic non-invasive monitoring of cardiac output compared to standard hemodynamic monitoring (only heart rate and blood pressure);
- Verify the relationship between standard hemodynamic monitoring (only heart rate and blood pressure) and continuous hemodynamic monitoring of cardiac output plus heart rate and blood pressure and the use of vasopressors, blood transfusion, infused volume;
- Evaluate complications of the anesthetic blockade technique with sedation over the blockade technique and general anesthesia;
- Assess postoperative pain, length of stay post anesthetic recovery and length of hospital stay between groups;

3. MATERIALS AND METHODS

3.1. Design of study

This is a prospective, randomized controlled trial comparing two anesthetic techniques using a standard and continuous hemodynamic monitoring device for cardiac output: sedation and interscalene block with general anesthesia and interscalene block for arthroscopic shoulder surgery.

3.2. Study Local

The research will be carried out in three tertiary hospital in the São Paulo city

3.3. Study Population

This Study was approved by the Ethics Committee for the Analysis of Research of the Hospital Sepaco by opnion number: 5.283.169 and CAAE: 54549221.0.1001.0086; of the Hospital das Clínicas, Faculty of Medicine, University of São Paulo – USP by opnion number: 5.103.355 and CAAE: 46436721.4.0000.0068 and of the Institute of Medical Assistance to the State Public Servant of São Paulo by opnion number: 5.189.754 and CAAE: 52984221.5.1001.5463. All patients submitted to arthroscopic shoulder surgeries in a beach chair position at this institutions who meet the inclusion criteria listed will be included.

3.4. Inclusion criteria

- Patients of both genders, over 18 years of age;
- Patients undergoing arthroscopic shoulder surgery in a beach chair position.

3.5. Exclusion Criteria

- Patients classified as emergency,
- Blood dyscrasia
- Refusal of the procedure
- Infection at the puncture site
- Allergy to the medication used
- Previous cerebrovascular disease

- History of orthostatic hypotension
- Pulmonary disease
- Chronic use of opioids
- Performance of arthroscopic surgeries on both shoulders
- Refusal to participate in the study and/or not to sign an informed consent form

3.6. Calculation of the sample size

Based on the sample calculation, the study by Soeding PF et al, 2011 (22) , which observed a drop in MAP under general anesthesia of approximately 30%, the study by Vincent S et al, 2005 (24) , which observed a decrease in MAP under sedation of 5.6%, and the study by Meidert et al 2017 (25) , which observed a decrease in SBP of 18 mmHg and 12 mmHg of MAP in the group with intermittent monitoring in relation to the group with continuous monitoring. Based on these data, a difference in mean total MAP between groups of 12 mmHg was used and therefore, considering the study power of 80% and alpha error of 0.025 by Bonferroni correction due to be divided into 4 groups, a total sample of 92 patients will be need, with standard deviation of the group with continuous monitoring of cardiac output of 10 mmHg and in the group standard monitoring of 15 mmHg. However, estimating that we may have losses, the final sample will reach 100 patients, so there will be 25 patients in each of the 04 groups.

3.7. Technician

The selected patients will be divided into two groups: group 1 general anesthesia + interscalene brachial plexus block and group 2 sedation + interscalene brachial plexus block. Each group will be divided into two groups, one with hemodynamic continuous monitoring and one with standard hemodynamic monitoring, totaling 4 groups in total in the study. Group 1A general anesthesia + interscalene brachial plexus block with continuous monitoring; group 1B general anesthesia + interscalene brachial plexus block with standard monitoring; group 2A sedation + interscalene brachial plexus block with continuous monitoring; group 2B sedation + interscalene brachial plexus block with standard monitoring (figure 1).

General anesthesia will be done with Propofol (1-3mg/kg), Fentanyl (1-6 mcg/kg) and Rocuronium (0.3-0.6mg/kg) and maintenance of anesthesia will be with Sevoflurane

and Remifentanil. The patient will be maintained on volume-controlled mechanical ventilation (tidal volume 6-8ml/kg, PEEP=5 mmHg, RR=12 ipm, FiO₂=50%) during the procedure. Parameters will be adjusted as assessed by the responsible anesthesiologist.

The technique of interscalene level brachial plexus block will be the same in both groups. The patient will be initially positioned in horizontal dorsal decubitus with the head slightly turned to the opposite side with slight elevation, with palpation of the interscalene groove and introduction of the needle in a slightly dorsal and caudal medial direction. The block will use a short Stimuloplex A50 needle (22G x 2") and the aid of Ultrasonography and peripheral nerve stimulator. The local anesthetic will be 0.5% ropivacaine 15-20 ml.

Sedation will be done with Propofol in a controlled target infusion pump.

The procedure should start about 15 minutes after the end of anesthesia.

Continuous monitoring will be done with clearSight continuously assessing blood pressure, cardiac output and heart rate; NIRS electrode to assess cerebral O₂ saturation, peripheral O₂ saturation, BIS value and axillary temperature.

Standard monitoring will be done with non-invasive blood pressure, heart rate, NIRS electrode to assess cerebral O₂ saturation, peripheral O₂ saturation, axillary temperature, BIS value. In addition, patients will use ClearSight, but the device will be blind to the anesthesiologist. Pressure monitoring will be every 5 min.

Hypotension will be considered with MAP lower than 65mmHg or a drop of 20% of the initial mean arterial pressure value based on the articles: Soeding PF et al 2011 (22) , Vincent S et al 2005 (24) and Meidert et al 2017 (25) . Cerebral O₂ saturation (rScO₂) was considered decreased when less than 60% or 20% lower than the baseline value, based on the article Moerman et 2012 (26) .

In the patient with continuous monitoring, decreased cardiac index (CI <2.6) or decreased cerebral saturation will be initially reversed with administration of 250ml fluid for 5 – 10min, if there is reversal of the picture, 20% increase in rScO₂ or rScO₂> 60% and/or CO>15%, the continuous monitoring is maintained. If there is no reversal, ephedrine 5mg is administered if hypotension remains, assess the hemoglobin (Hb) level. If Hb<9, perform 1CH transfusion, if Hb greater than or equal to 9, perform dobutamine infusion (titrate dose of dobutamine), maintaining monitoring (figure 2). In addition, a patient with hypotension is initially reversed with 250ml fluid for 5 to 10min, if there is a reversal of the condition, monitoring is maintained. If there is no improvement, administer ephedrine 5mg. If you maintain hypotension, check your hemoglobin level. If

hb<9, perform 1CH infusion. If hb greater than or equal to 9, perform norepinephrine infusion (titrate dose of norepinephrine), maintaining monitoring (figure 2).

[figure not shown]
In the patient with standard monitoring, if hypotension, administer 250ml fluid for 5 – 10min, if there is a reversal of the condition, maintain monitoring. If there is no improvement, administer ephedrine 5mg. If you maintain hypotension, check your hemoglobin level. If hb<9, perform 1CH infusion. If hb greater than or equal to 9, perform norepinephrine infusion (titrate dose of norepinephrine). If there is a decrease in rScO₂, evaluate the MAP. If hypotension, follow the hypotension flowchart detailed above. If you do not have hypotension and the patient is on OTI, evaluate capnography, O₂ flow (FiO₂), hypovolemia and anemia. If there is no hypotension and the patient is under sedation, it assesses level of consciousness, O₂ flow (FiO₂), hypovolemia and anemia (figure 3 and 4).

The anesthetic management of patients will be the responsibility of anesthesiologists.

BIS will be considered normal value between 40 and 60.

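### A fall in cerebral saturation without hypotension leads by rule to fluid in the continuous arm but only to assessments in the standard arm, so differences in infused volume and rScO₂ cannot be credited to cardiac-output monitoring alone

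*Combined protocol and SAP*

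**What the plan says.** Section 2.2 sets three aims that bear on this point. One is to "Verify the superiority of continuous hemodynamic non-invasive monitoring of cardiac output compared to standard hemodynamic monitoring". A second relates the type of monitoring to "and the use of vasopressors, blood transfusion, infused volume". A third is to "Compare changes in cerebral tissue saturation between groups".

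Section 3.7 lists the equipment. The continuous arm has ClearSight and "NIRS electrode to assess cerebral O₂ saturation, peripheral O₂ saturation, BIS value and axillary temperature". For the other arm: "Standard monitoring will be done with non-invasive blood pressure, heart rate, NIRS electrode to assess cerebral O₂ saturation", together with the remaining standard monitors. Standard-arm patients also wear ClearSight, but its display is hidden from the anesthesiologist. No such concealment is stated for NIRS.

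Section 3.7 then gives one definition of decreased rScO₂ for all patients (below 60%, or 20% below baseline) and a different response in each arm. Continuous arm: "decreased cardiac index (CI <2.6) or decreased cerebral saturation will be initially reversed with administration of 250ml fluid", with further steps if there is no reversal. Standard arm: "If there is a decrease in rScO₂, evaluate the MAP". Hypotension there leads to the hypotension pathway, which also begins with 250 ml. Without hypotension, the text lists things to assess: capnography in intubated patients or level of consciousness in sedated patients, and in both FiO₂, hypovolemia and anemia. The section adds that anesthetic management is the anesthesiologist's responsibility.

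**The concern.** The monitoring objectives ask what is gained by seeing cardiac output. For the arms to answer that, they should differ in whether cardiac output is seen and in what follows from seeing it. Here they also differ in the written response to a signal that both anesthesiologists can see and that does not come from the cardiac-output device.

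That response feeds into two compared quantities. The fluid step adds directly to infused volume, and it is given in order to raise rScO₂. So rScO₂ is an outcome in both arms but a stand-alone treatment trigger in only one. Randomization does not remove this, because the difference is part of the assigned arm.

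Section 3.13 plans comparisons of standard with continuous monitoring and makes no provision for it. Section 3.10 records volume, vasopressors and blood components but does not list what prompted each one, so the contributions could not be separated afterwards. At stake is the interpretation of the monitoring comparison: a favorable difference could be credited to cardiac-output monitoring when part of it comes from the rule for NIRS.

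**Working it through.** The plan gives no figure on this point, and the sample size in section 3.6 is not in dispute. The check sets the written first responses in section 3.7 side by side.

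| Patient state | Continuous arm | Standard arm | Source of any difference |
|---|---|---|---|
| Hypotension, with or without an rScO₂ fall | 250 ml | 250 ml | None in the written first step |
| No hypotension, CI below 2.6 | 250 ml | CI hidden, no CI-triggered step | Cardiac-output display: a legitimate effect |
| No hypotension, CI not below 2.6, rScO₂ decreased | 250 ml | Assessments only | Rule for a signal visible in both arms |

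Only the last row confounds. The standard-arm algorithm acts on rScO₂, so the anesthesiologist must be able to see it there.

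**Later steps.** In the continuous-arm CI/rScO₂ branch, the condition about persisting hypotension sits between the ephedrine step and the hemoglobin step, and the punctuation does not settle which it governs.
- If it governs the hemoglobin step, a normotensive patient whose rScO₂ does not recover gets ephedrine by rule, and the transfusion or dobutamine steps require hypotension.
- If it governs ephedrine, that patient gets no ephedrine by rule.

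On neither reading does a normotensive patient pass through the whole ladder by rule. The fluid step is the only one clearly free of a hypotension condition.

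**Size of the fluid effect.** Inputs:
- 250 ml per episode (section 3.7).
- 50 patients per monitoring arm: two groups of 25 (section 3.6).
- p, the share of continuous-arm patients with one episode of the last-row kind. The documents do not give it; 5-30% is an assumption.
- No discretionary fluid for such episodes in the standard arm (assumption).

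Mean shift in infused volume = 250 ml × p.

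| p | Expected patients of 50 | Mean shift per patient |
|---|---|---|
| 5% | 2.5 | 250 × 0.05 = 12.5 ml |
| 10% | 5 | 250 × 0.10 = 25 ml |
| 20% | 10 | 250 × 0.20 = 50 ml |
| 30% | 15 | 250 × 0.30 = 75 ml |

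Repeat episodes would raise these values; discretionary fluid in the standard arm would lower them. The documents give neither a standard deviation nor a relevance threshold for infused volume, so the shift cannot be rated as large or small. The effect on rScO₂ cannot be computed from the documents.

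**The case against.** The strongest reply is that a monitor works only through the response to it. Section 3.7 sets out each arm's algorithm openly, so calling the contrast a strategy may seem mere labelling. That holds for cardiac index, which is hidden in the standard arm: fluid given for low CI is the effect of seeing it. It does not hold for rScO₂, which both arms see.

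Discretion is a fair limit. The standard arm must consider hypovolemia and anemia, and the anesthesiologist may then give fluid. The flowcharts for this branch are not shown and may contain a further step. Both could shrink the difference. Neither removes the asymmetry in the text.

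Several stronger readings are tempting but not supported:
- A reader might infer that rScO₂ never leads to fluid in the standard arm. It does when hypotension is present.
- A reader might infer that ephedrine, transfusion and dobutamine are all built in for normotensive patients. The hypotension condition gates at least part of that ladder.
- A reader might infer that section 2.2 contradicts itself by describing standard monitoring as heart rate and blood pressure only while NIRS is used. The Introduction and the general objective treat cerebral oxygenation separately, so the phrase can describe the hemodynamic component alone.
- A reader might infer that the protocol counts fluid or vasopressor use as proof of superiority. The superiority objective names no such endpoint; their relationship to monitoring is a separate objective.
- A reader might infer that comparing only hypotension-triggered treatment would isolate the monitoring effect. Pressure is read continuously in one arm and every 5 min in the other, and earlier fluid for CI or rScO₂ may prevent later hypotension.

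**Conclusion.** The concern holds for the rScO₂ branch. On the text of section 3.7, a fall in rScO₂ by itself, without hypotension, leads by rule to 250 ml in the continuous arm and only to assessments in the standard arm. Differences in infused volume and rScO₂ therefore cannot be attributed to cardiac-output monitoring alone. The same may apply to vasopressor use, but less certainly, because the ephedrine wording is ambiguous.

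The built-in shift in mean infused volume is 12.5-75 ml per patient if 5-30% of continuous-arm patients have one qualifying episode and the standard arm gives no discretionary fluid. Both conditions are assumptions. The conclusion about attribution does not depend on the exact size. As written, the design supports a comparison of two monitoring-plus-treatment strategies. This should be corrected because it changes what the trial can conclude; it does not invalidate the trial or its sample size.

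**What to change.** Do one of the following:

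1. Reconcile the two responses to an rScO₂ fall in section 3.7. Which response applies is the sponsor's clinical choice.
2. Keep both and declare them part of the intervention. Restate the monitoring objectives in section 2.2, and the planned conclusion, as the continuous-monitoring strategy (ClearSight display plus its CI/rScO₂ algorithm) against the standard strategy. Report fluid, vasopressor, dobutamine and transfusion as treatment delivered under each strategy.

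In either case, clarify which step the hypotension condition governs in the continuous-arm CI/rScO₂ branch. Add to section 3.10 a case-report field for the trigger of each intervention (hypotension, CI or rScO₂), and to section 3.13 a table of interventions by trigger and arm. Label that table descriptive, because hypotension is detected on different schedules in the two arms.

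The second option costs the rewording of the monitoring objectives, one data field and one table, with no change to arms or sample size. Its downside is a narrower claim.

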3.9. Project flowchart

The project flowchart according to CONSORT, follows below:

3.10. Data collect

After receiving an explanation about the procedures to be performed and signing the consent form, patients will be allocated into 4 groups as explained above using a table of random numbers. Data collected will be age, weight, height, race, gender, ASA, comorbidities, medications in use. During the surgical procedure, the analyzed data will be medications, infusion volume, blood components, vasopressor, anesthetic and surgical complications, anesthesia and surgery time.

In addition, systolic, diastolic and mean blood pressure, heart rate, cerebral O₂ saturation, peripheral O₂ saturation, axillary temperature, BIS value, cardiac index (in patients who will use clear sight) and et CO₂ (in patients who will be intubated) every 5 min intraoperatively and during post-anesthetic recovery (PAR) (27).

Postoperatively, the data analyzed will be: anesthetic recovery time, hospital stay, need to be referred to the intensive care unit (ICU), length of stay in the ICU and if the patient died. In addition, the visual numerical pain scale and the descriptive verbal pain scale will also be evaluated in the PVR and 24 hours after the procedure (28).

Sedation assessment will be performed using the intraoperative RASS scale for patients who are allocated to the sedation + interscalene brachial plexus block group and postoperatively for all groups. The values of the RASS scale are shown in table 1. The Confusion Management Method in the ICU (CAM-ICU) scale will be used to assess delirium, the table with the parameters used will be shown in figure 5 (29);(30).

3.11. Study blinding

The study will be covered in the assessment of cardiac output during intraoperative data analysis for standard monitoring group. In addition, data analysis will be covered, and they will just be identifying groups by numbers.

3.12. Randomization

Randomization will be done in blocks, the randomization list will be a random sequence of blocks of participants. Blocks will have the same predetermined size with 8 participants in a block, with four possible intervention and control sequences.

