3.13. Data analysis

Categorical variables will be presented as absolute and relative frequencies.

Quantitative variables will be presented as mean and standard deviation or as median and interquartile range when appropriate. We will use the Kolmogorov-Smirnov test to assess the distribution pattern of continuous numerical variables.

Comparisons between general anesthesia + block and block + sedation will be performed, as well as comparisons between standard and continuous monitoring. Proportions will be compared using the Chi-square test or Fisher's exact test, if the assumptions for using the Chi-square are violated. Quantitative variables will be compared using the Mann-Whitney test or irregularly distributed Anova when appropriate.

Variables with repeated measurements will be analyzed by linear general multiple model (GLM) with Bonferroni correction for P values.

The association between explanatory variables and response will be evaluated using logistic regression models. Variables selected in the bivariate analyzes ($p<0.05$) and those considered clinically relevant will be submitted to multiple logistic regression analyses. Variables with substantial collinearity will be excluded. The result of logistic regression analyzes will be expressed as odds ratios and respective 95% confidence intervals.

All significance probabilities (P values) presented will be two-tailed. P values will be considered statistically significant when less than 0.05. *The Statistical Package for Social Sciences* software version 26.0 (SPSS Inc.®; Chicago, IL, USA) will be used to perform the analyses.

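### One printed block size of 8 and no hospital term or stratum in a three-hospital trial with unmasked technique: the likely bias is small, but precision is lost if hospitals differ and some allocations can be known in advance

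*Combined protocol and SAP*

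**What the plan says.** Section 3.12 describes a blocked list: "Blocks will have the same predetermined size with 8 participants in a block, with four possible intervention and control sequences". It speaks of the list in the singular and names no hospital stratum. Section 3.2 states: "The research will be carried out in three tertiary hospital in the São Paulo city". Section 3.10 places allocation after consent: "patients will be allocated into 4 groups as explained above using a table of random numbers". No list-holder, envelope or central release appears in the visible text; the CONSORT flowchart and Figure 1 are not shown.

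On masking, Section 3.11 states: "The study will be covered in the assessment of cardiac output during intraoperative data analysis for standard monitoring group". It also masks group labels at analysis, and Section 3.7 hides the ClearSight device from the anesthesiologist in the standard-monitoring groups. Nothing masks general anesthesia against sedation, and Section 3.7 adds: "The anesthetic management of patients will be the responsibility of anesthesiologists".

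For analysis, Section 3.13 states: "Variables with repeated measurements will be analyzed by linear general multiple model (GLM) with Bonferroni correction for P values". Two-group comparisons use Mann-Whitney or ANOVA, chi-square or Fisher. No hospital term is named for any of these. The logistic models admit clinically relevant variables, so hospital could enter there, but it is not named.

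**The concern.** There are two separate issues.

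**Prediction.** A single known block size lets anyone who has seen the earlier allocations work out some of the next ones. The person giving the anesthetic cannot be masked to technique. The Introduction says the hemodynamic changes of the beach chair position are enhanced by general anesthesia, especially in elderly and hypertensive patients, and both traits can be seen at recruitment. If an anticipated allocation affected who was approached or when, the MAP comparison between techniques would shift, and the stated analysis could not remove the shift.

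**Precision.** One list shared by three hospitals balances technique overall but not within each hospital. That does not bias a valid randomisation. If hospitals differ in MAP, however, an analysis that omits hospital leaves that variation in the error term.

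**Working it through.** **Inputs from the plan.** Section 3.6: SDs of 10 and 15 mmHg, a MAP difference of 12 mmHg, alpha 0.025, power 80%, 92 patients before losses and 100 after. Section 3.12: block size 8. Section 3.2: three hospitals.

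**The plan's own figure.** Pooled SD = √((10² + 15²)/2) = √162.5 = 12.75 mmHg. A two-sided t-test calculation at alpha 0.025 needs 23 per group (power 80.1%), and 4 × 23 = 92. The stated figure reproduces, and the sample size is not in dispute.

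**Standard error of the technique comparison (50 against 50).** 12.75 × √(2/50) = 12.75 × 0.2 = 2.55 mmHg.

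**Predictability of a block of 8 (4 per technique), all balanced orders equally likely.**
- Full view of earlier allocations: expected correct guesses = 4 + 2⁷/C(8,4) − ½ = 4 + 128/70 − 0.5 = 5.33 of 8, or 66.6%. Fully determined positions = 8/5 = 1.6 of 8, or 20%.
- Shared list, with a site seeing an assumed one third of it and knowing the position in the block: 55.4% (simulation, 200,000 blocks).

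**Bias and type I error.** Let D be the mean MAP difference between patients approached under opposite guesses. D = 2 to 5 mmHg is an assumption; the documents give no value. If staff act on every guess, bias = D × (2p − 1). If they act only when certain, bias = D × P(certain). Two-sided type I error is at nominal 5% with SE 2.55.

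| Situation | Bias, mmHg | Type I error |
|---|---|---|
| One-third view of a shared list (p = 0.554) | 0.22 to 0.54 | 5.1 to 5.5% |
| Full view, certain guesses only (0.20) | 0.40 to 1.00 | 5.3 to 6.8% |
| Full view, every guess acted on (p = 0.666) | 0.66 to 1.66 | 5.8 to 10.0% |

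At the planning alpha of 0.025, the first row becomes 2.6 to 2.8%.

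**Hospital gaps under one shared list.** Assumed hospital sizes are 34/33/33, 50/30/20 and 60/25/15, with 10,000 simulated trials each. The difference in numbers between techniques averages 3.5 to 3.8 patients per hospital, and some hospital has a gap of 8 or more in 20-28% of trials.

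**Precision without a hospital term.** SE = 0.2 × √(162.5 + V), where V is the between-hospital variance and 12.75 is taken as the within-hospital SD.
- Means −5/0/+5: V = 13.7 to 16.8, SE = 2.65 to 2.68, a rise of 4-5% over 2.55.
- Means −10/0/+10: V = 54.8 to 67.0, SE = 2.95 to 3.03, a rise of 16-19%.

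With a hospital factor and a shared list, information is 24.5 of 25, a loss of 0.5/25 = 2%. SE is then 2.55 × √(25/24.5) = 2.58, whatever the hospital means.

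**Do balanced lists rescue the unadjusted tests?** No. For an assumed 7 mmHg effect, simulated Mann-Whitney power is about 71% with a shared list and 72% with separate lists at −5/0/+5, and about 60-62% with either at −10/0/+10.

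**Effect of varying the blocks.** For a 33-patient list seen in full by someone who knows the candidate sizes, fixed 8 gives 66% correct and 19% certain; 8 and 12 in random order gives 64% correct and 6% certain. Acting only on certain guesses, bias falls from 0.4-1.0 to 0.1-0.3 mmHg. Hiding the size alone does not lower overall guessing: always naming the less-used technique still scores 66% on blocks of 8.

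**The case against.** The strongest case against is that the block size is not the main weakness. Varying it lowers overall guessing by only two percentage points, and with concealed release a fixed block of 8 does little harm. That stands, and it is why the hospital analysis comes first in the fix. The absence of a release procedure from the visible text is missing detail. A reader might infer that allocation was unconcealed; the documents do not say so, and some figures are not shown.

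Second, the two harms pull in opposite directions. The 66.6% figure needs a list per hospital, or staff who see all three sites; the hospital gaps need one shared list. This also stands. Section 3.12 speaks of one list, so the partial-view row is the natural one. A reader might take the 10.0% type I error as the finding. It needs full view, action on every guess and the top of an assumed range, and the documents support none of these.

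Third, no section says that the anesthesiologists recruit. Consent precedes allocation, and Section 3.3 states: "All patients submitted to arthroscopic shoulder surgeries in a beach chair position at this institutions who meet the inclusion criteria listed will be included". These limit steering but do not hide the next allocation.

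Fourth, the SDs in Section 3.6 are not labelled as within-hospital. If they already include hospital differences, the SE without a hospital term is at most 2.55, and the cost appears instead as a failure to go below it. The 12 mmHg is also a poor yardstick here, since its source compared monitoring methods rather than techniques.

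Finally, a reader might take the four sequences literally. If only four fixed orders existed and were known, about 80% of positions would be determined (simulation). The text does not establish that: Section 3.7 describes two techniques by two monitoring methods, "totaling 4 groups in total in the study", and the phrase may simply mean those groups. It is unclear and needs clarifying, since every predictability figure above assumes that all balanced orders are possible.

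**Conclusion.** The point holds as a recommended change, not as evidence of serious bias. On the shared-list reading, selection bias would be about 0.2 to 0.5 mmHg with type I error of 5.1-5.5%, given the assumed one-third view and the assumed 2 to 5 mmHg steering difference. The firmer part is the analysis: three hospitals, no hospital term, and a standard error 4-5% or 16-19% higher under the two assumed sets of hospital means, with 12.75 mmHg taken as the within-hospital SD. If hospitals do not differ, nothing is lost by omitting hospital, and including it costs about 2% of information. Confidence is medium, because the size depends on quantities that the documents do not give.

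**What to change.** 1. **Analysis, whatever the recruitment status, before data are analysed.** Include hospital as a factor in the repeated-measures GLM and in the regression models. Replace the plain Mann-Whitney test with the van Elteren test, and chi-square/Fisher with Cochran-Mantel-Haenszel, both stratified by hospital. Cost: two model degrees of freedom and a short amendment.
2. **Patients not yet randomised.** Use permuted blocks of 8 and 12 in random order, all balanced orders equally likely, with the sizes kept out of documents that enrolling staff see. The gain is in certain guesses (about 19% to 6%), not in overall guessing (66% to 64%). Cost: a new list.
3. **State the list structure.** Either keep one central list and rely on the hospital factor, at about 2% of information; or stratify by hospital with concealed release by someone outside enrolment and anesthesia, after eligibility, consent and baseline data are recorded. Concealed release must accompany separate lists, because they show each site its whole sequence (64% guessed, against 55% with a third of a shared list). Separate lists also widen the average overall technique gap from 1.0 to about 1.8 patients.
4. **Wording.** Say what the four sequences are. If the four groups are meant, state equal allocation to 1A, 1B, 2A and 2B. Describe the release procedure actually used.
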